7.5 Treatment

The treatment areas are divided into 3 groups. Each Subjects will be allocated to one of the following groups::

- Two small anatomical areas (right and left axillae and double sided bikini line) or;
- One double sided large area (right and left thighs) or;
- One large area (whole back / abdomen)

Other areas not defined above, as face, are not allowed to be treated.

Each site will recruit four subjects for each one of the three treatment groups (as specified above or in this section)

Based on the mild nature of treatment, anesthesia is not required. Treatment procedure should include positioning of the patient in a manner that enables access to the treated anatomical site. The positioning of subjects during treatment will be contingent on the location of the treated anatomical site.

Before starting treatment apply a layer of conductive gel to the treatment area.

After applying the conductive gel, locate the applicator in close contact, perpendicular to the skin with no pressure applied. Pressing the applicator will fire the IPL pulse. In order to ensure full coverage of the treatment area applicator placement should overlap approximately 1/3 of the previously treated skin.

During whole treatment duration, the safety of the subject and study personnel must be secured via the use of adequate safety eye protection.

During whole treatment duration, subject reaction must be monitored and if the subjects report an intolerable level of pain, treatment shall be ceased immediately. The treatment session will last until the required treated area is covered.

The normal response to these treatments is transient erythema and edema. If any side effects occur, as indicated in the protocol, they will be recorded.

7.6 Post-treatment Instructions

7.6.1 Post treatment

The assessment of pain based on the subject's report will be documented immediately after each treatment test spot in the anatomical area treated. The Investigator should also examine and record the skin immediate response following treatment.

Cold packs may be placed on the treated area for post-treatment cooling. On the night following treatment, subjects should generally avoid hot water, cleanse their skin gently with tepid water, and hydrate the skin with a suitable moisturizer.

Subjects should be aware that post-treatment erythema, edema and some discomfort of the treated areas are possible and should not be a cause for concern. They may also experience some purpura in the treated areas which would be expected to resolve within several days.

Subjects will have to be instructed not to tweeze, pluck, wax, use depilatory creams, or any other hair removal methods in the treated areas throughout the evaluation. Seven days prior to each treatment and follow-up visits subjects shall not shave the treatment areas in order to obtain accurate hair counts.

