4.1 Primary Effectiveness Endpoints

- Hair count reduction, as calculated from photographs and defined as (count-baseline)/baseline*100; 3 months following the last treatment FU2 (hair removal).

- Hair count reduction, as calculated from photographs and defined as (count-baseline)/baseline*100; 6 months following the last treatment FU 3 (permanent hair reduction).

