7.3 Screening Procedures

7.3.1 Subject Enrollment

If the subject has met the preliminary study criteria the study doctor, and/or his designee, will obtain an informed consent from the subject, clearly indicating his/her understanding of the requirements and possible risks involved with study participation and other applicable treatment options.

During the first visit, the study investigator, and/or his designee, will screen the subject for eligibility to participate in the clinical study using the Inclusion, Exclusion criteria. During screening the study doctor will review the subject's medical history, and examine the subject's targeted area to ensure that it meets the study criteria. The subject will complete screening and the treatment will be scheduled. Treatment may be performed on the day the subject was enrolled or no later than one week following enrollment and screening.

During the first visit, the investigator will ask women of child-bearing potential for the date of their last period, if not applicable the investigator shall inquire about the form of contraceptive they use to confirm they meet the inclusion criteria.

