7.4 Pre-Treatment Procedures

7.4.1 Subject Skin care and medication

- Subjects will be instructed to avoid sun exposure for at least four weeks before treatment and to use broad spectrum sunscreen of no less than 30 SPF on a daily basis, replenishing it as often as needed throughout the course of the study. In addition Tanning is to be strictly avoided.
- Subjects should not pluck, tweeze, wax, use depilatory creams, electrolysis, hair bleaching agents, hair growth inhibitors (such as Vaniqa®) or any treatment with a laser or other devices in the study treatment throughout the course of this study and follow-up examinations.
- Immediately before treatment, the area will be shaved to the skin surface using foam or gel to minimize skin irritation.

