7.4.2.2 Hair count

The customized hair count sticker templates detailed in section will be supplied by the sponsor. Templates consist of a rectangular frame sticker with a one square inch rectangular window (25.4mm x 25.4mm). The sticker template will be placed directly on the skin and the hairs in this window will be counted at specific visits during the study as detailed in section 7.2.1.1. For identification, the subject's ID, treatment area and visit date shall be filled out on the designated area upon the template frame.

The following procedure is intended to ensure that the template is placed in the same position during subsequent visits:

7.4.2.2.1 Baseline visit (prior to the 1st treatment):

1. The appropriate treatment area will be decided.
2. The hair in the area to be treated will be scissor trimmed to 2 mm to facilitate hair counts for photography.
3. The template will be completed with the subject ID, treatment area and date.
4. The template will be placed directly on the skin, in the area to be treated.
5. A clear transparency sheet will be placed over the treatment area, over the template.
6. The transparency sheet will be marked with a permanent marker to indicate anatomical landmarks and the sticker template location.
7. A general photograph of the sticker template, overlaid with the transparency sheet will be taken, as well as a close-up picture.
8. The transparency sheet will be removed and an additional close-up picture of the sticker template will be taken for the baseline hair count.

7.4.2.2.2 "Hair count" treatment visits [3, 6, 1M±7D FU1, 3M±7D FU2 and 6M±7D FU 3]:

1. The hair in the area to be treated will be scissor trimmed to 2 mm to facilitate hair counts from photography.
2. The template will be completed with the subject ID, treatment area and date.
3. The sticker template will be placed on the area to be treated using anatomical landmarks and the baseline picture to properly position the transparency sheet prepared in the baseline visit.
4. A close-up photograph of the sticker template will be taken.
5. The sticker will then be removed, the area shaved to the skin surface and treatment performed.

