Appendix I Study Flow Chart

Study Activities	Visit #0*	Visit #1***	Visit #2	Visit #3	Visit #4	Visit #5	Visit #6	Visit #7§	Visit #8§	Visit #9§§
	Pre-Tx	Tx #1 Up to 7 days after Visit 0	Tx #2 4-6 WKS POST Tx1	Tx #3 4-6 WKS POST Tx2	Tx #4 4-6 WKS POST Tx3	Tx#5 -6 WKS POST Tx4	Tx #6 4-6 WKS POST Tx5	FU #1 1M±7 D FU	FU #2 3M±7 D FU	FU #3 6M±7 D FU
Qualify for study: Informed Consent, Eligibility assessment, Demographic information, Medical history & treatment related medical examination	X									
Test spots**		X Pre-Tx								
Photographs	X			X Pre-Tx			X Pre-Tx	X	X	X
Treatment		X	X	X	X	X				
Immediate and short term response		X	X	X	X	X	X			
Hair Count by study personnel	X			X			X	X	X	X
Hair Count by blinded evaluators (to be conducted post study)	X							X	X	X
Subject's comfort assessment		X	X	X	X	X				
Subject's improvement/satisfaction				X			X	X	X	X
Adverse events recording		X	X	X	X	X	X	X	X	X
Study termination										X

* Visit #0 includes various screening activities and explanations to the candidate regarding the evaluation; should the subject sign the Informed Consent Form, complete the test spot procedure and undergo treatment during Visit #0, it will effectively become merged with Visit #1.

** Test spots should be performed prior to Tx #1 and with any treatment parameter alternation later on in treatment regime.

*** An Intermediate Safety report will be performed following Tx #1.

§ A Hair Removal report will be performed following FU #1 and FU #2 of 1M ±7D; 3M ±7D.

§§ A Permanent Hair Reduction report will be performed following FU #3 of 6M±7D.

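### No minimum regrowth time is ensured before the Visit 0 baseline photograph, so baseline and follow-up hair counts may not be comparable and both primary percent changes may be biased in either direction

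*Combined protocol and SAP*

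**What the plan says.** **The counting condition.** Section 7.6.1, within the post-treatment instructions, states: "Seven days prior to each treatment and follow-up visits subjects shall not shave the treatment areas in order to obtain accurate hair counts".

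**When the baseline is taken.** Appendix I marks the photograph, the study personnel's count and the blinded evaluators' count at Visit 0, together with consent and eligibility. None of the three is marked at Visit 1. Section 7.4.2.2.1 places the baseline before the first treatment without fixing a day.

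**When treatment 1 follows.** Section 7.3.1: "Treatment may be performed on the day the subject was enrolled or no later than one week following enrollment and screening". The column header in Appendix I agrees: "Tx #1 Up to 7 days after Visit 0". A footnote there covers subjects who consent and continue on the same day: "complete the test spot procedure and undergo treatment during Visit #0, it will effectively become merged with Visit #1".

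**Other hair removal.** Section 7.4.1 begins its list of bans with "Subjects should not pluck, tweeze, wax, use depilatory creams" and applies it during the study and follow-up. Before enrolment, exclusion 26 restricts only laser and other devices, for six months.

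**Preparation for the photograph.** At baseline: "The hair in the area to be treated will be scissor trimmed to 2 mm to facilitate hair counts for photography". The same trim is specified at later count visits. Section 5.1 requires visible hair, and inclusion criterion 3 requires more than 15 terminal hairs in the count site.

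**Use of the count.** Section 4.1 defines both primary endpoints, at FU2 (3 months) and FU3 (6 months), as the change from baseline divided by baseline, times 100. Section 2 calls the study baseline-controlled. Section 8.3 compares baseline with follow-up by paired tests.

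**The concern.** The protocol itself says that unshaved time matters for an accurate count, then schedules the one count used in every comparison at a visit the rule does not clearly reach. A subject first seen at Visit 0 may have shaved recently, may have waxed some weeks before, or may not have removed hair for a long time. The photograph records whatever has emerged.

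The baseline is the denominator of both primary endpoints, so a difference in regrowth goes straight into the percent change. No untreated area is followed in parallel, and a paired test cannot separate a treatment effect from a systematic difference in visible hair. Blinding does not help, because the blinded evaluators count what the photograph shows. If time since hair removal was not recorded at baseline, it cannot be recovered at analysis.

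**Working it through.** **1. The plan's own figures.** The documents give no regrowth time at baseline, no share of hairs visible and no standard deviation, so there is no stated figure for this point to reproduce. The sample sizes used below come from Section 8.2: 3 × 40 = 120.

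**2. How much of the no-shave period precedes the photograph.** Read literally, the rule covers the seven days before treatment 1. If treatment 1 is g days after Visit 0, the part of that period lying before the Visit 0 photograph is max(0, 7 − g) days.

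| g (days) | Days before the photograph |
|---|---|
| 0 (merged visits) | 7 |
| 3 | 4 |
| 7 | 0 |

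At g = 0 all seven days are covered, but they precede consent, so no instruction given as part of the study can have secured them. At g = 7 the rule places no condition on the photograph.

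**3. Effect on the endpoint.** Let R be the true proportional reduction, and vB and vF the shares of hairs visible at baseline and follow-up. Then

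observed percent change = 100 × [(1 − R)/(vB/vF) − 1].

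R and vB/vF are assumptions.

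| vB/vF | R = 0 | R = 30% |
|---|---|---|
| 0.8 | +25.0% | −12.5% |
| 0.9 | +11.1% | −22.2% |
| 1.0 | 0.0% | −30.0% |
| 1.1 | −9.1% | −36.4% |
| 1.2 | −16.7% | −41.7% |

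For example, with R = 0 and a ratio of 1.1, 100 × (1/1.1 − 1) = −9.1%. With equal regrowth (ratio 1.0) the formula returns the true change.

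If only half the subjects are affected and R = 30%, a ratio of 0.8 gives 0.5 × (−12.5) + 0.5 × (−30.0) = −21.3%, and a ratio of 1.2 gives −35.8%.

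**4. Effect on the test.** Take R = 0 and a systematic ratio of 1.05, so the mean shift is 100 × (1/1.05 − 1) = −4.8 points. Assume a standard deviation of the percent change of 15 to 35 points and use a normal approximation to the paired test at two-sided 5%. The chance of p < 0.05 is then 94% to 32% at n = 120 and 52% to 14% at n = 40. The test is at its nominal 5% only when the ratio is 1. These figures show sensitivity to the assumptions and do not estimate what happened in this trial.

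**The case against.** **The rule may already reach baseline.** It refers to each treatment, which literally includes treatment 1. When Visits 0 and 1 merge, the seven days before treatment are the seven days before the photograph. The protocol also sets other conditions that must be met before entry, such as sun avoidance and no artificial tanning, so pre-visit conditions are possible in principle. This partly stands: a site could screen for time since last shave. However, the rule sits among post-treatment instructions, no eligibility criterion asks about shaving or waxing, and the literal reading gives less cover the longer the gap to treatment 1.

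**There are safeguards.** Visible hair, more than 15 terminal hairs and the common 2 mm trim make a freshly shaved baseline unlikely, and the trim evens out the length of longer hair. That stands as a limit on extreme cases. These conditions do not fix regrowth time: a site with 60 hairs of which half have emerged shows 30 and qualifies, and trimming cannot reveal hairs not yet through the skin.

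**Stronger readings a reader might infer.**
- *That the primary result is biased, and in the device's favour.* The documents show that regrowth can differ, not that it does. Bias in the mean needs a systematic difference, and a shorter baseline regrowth would understate the reduction.
- *That every later count has a fixed seven-day regrowth.* Seven days is a minimum. FU2 and FU3 are three and six months after the last treatment, so the treatment-day shave does not set their regrowth, which can also be weeks.
- *That a real reduction could appear as an increase because half the baseline hairs are hidden.* Nothing in the documents supports so large a share across the study, and the safeguards make it less likely.

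**Conclusion.** The point holds in a limited form. As written, the plan can be followed exactly and still yield baseline and follow-up counts taken after different regrowth times, with no control area to absorb the difference and no record with which to adjust for it. Both primary percent changes may be biased, in either direction.

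The size is not computable from the documents. Under the assumed visibility ratios of 0.9 to 1.1, a null effect reads as anything from about an 11% increase to about a 9% reduction. This assumes that the ratio applies to all subjects; it shrinks in proportion if only some are affected and averages out to the extent that differences between subjects are not systematic. The gap should be closed, since the protocol already has the rule it needs and has only to apply it to baseline.

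**What to change.** - **Same condition at every count.** In Sections 7.4.2.2.1 and 7.6.1, apply to the baseline photograph the no-shave interval that applies before follow-up count visits, and extend the Section 7.4.1 hair-removal restrictions to the period before it.
- **Timing of the photograph.** Take it at Visit 1, before any test spot and before treatment 1. The order matters because Appendix I puts the test spots at Visit 1 and Section 7.4.3 places them within the area to be treated. Keep a Visit 0 photograph, and with it same-day merging, only for subjects who already meet the interval.
- **Record it.** At every count visit, ask about and record days since last shave and since any other hair removal. This also shows how far follow-up regrowth exceeds the minimum, and it allows a sensitivity analysis.
- **Reconcile the text.** Align Sections 7.3.1, 7.4.2.2 and 7.6.1 with Appendix I. A full seven days after Visit 0 fits the present window only on exactly day 7, so the Visit 0 to Visit 1 window needs a small extension, and more if the sponsor sets a longer washout for waxing or plucking.

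**Cost.** Wording changes and one or two case report form fields. Some subjects lose same-day treatment and scheduling becomes slightly longer. The planned 120 subjects are unaffected.

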7.7 Follow-up regimen

Follow-up visits will occur for all subjects one month FU1 (\pm seven days) three FU2 (\pm seven days) and six FU3 (\pm seven days) months after the last treatment as detailed in table 1 and Appendix I.

8 Study Analysis Plan

8.1 Study Hypothesis

The study will confirm that the Versa HR 690 nm applicator is safe for removal of unwanted hair, and will result in hair removal and permanent hair count reduction for patients with Fitzpatrick Skin Type V-VI.

8.2 Sample Size Justification

The proposed study sample of 120 subjects will be sufficient to evaluate the safety and the efficacy of the treatment using the HR applicator in 5 distinguished anatomical areas and to obtain qualitative assessments of comfort levels experienced during treatments. Based on previous experience with other IPL hair removal systems, low subject variance of the tested element, the proposed study sample of 40 subjects per each anatomical area (total of 120) will be sufficient to evaluate the safety and the efficacy of the treatment and to obtain qualitative assessments of comfort levels experienced during treatments.

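### Section 8.2 promises 40 subjects per anatomical area, but 120 is 40 per treatment group; separately, four per group at each of 20 sites gives 240 subjects, not 120

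*Combined protocol and SAP*

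**What the plan says.** Section 8.2 is the protocol's only sample-size statement. Its first sentence says that 120 subjects suffice for safety and efficacy "using the HR applicator in 5 distinguished anatomical areas". Its second says that "the proposed study sample of 40 subjects per each anatomical area (total of 120) will be sufficient to evaluate the safety and the efficacy". It gives no effect size, standard deviation or power.

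Section 7.5 sets out the design: "The treatment areas are divided into 3 groups", and "Each Subjects will be allocated to one of the following groups". The groups are:
- Group 1: "Two small anatomical areas (right and left axillae and double sided bikini line").
- Group 2: right and left thighs, as one double-sided large area.
- Group 3: "One large area (whole back / abdomen").

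Section 7.5 also has each site recruit four subjects for each of the three groups. The synopsis gives 20 sites and 120 subjects. The synopsis and Sections 2 and 5.1 put a ceiling of 12 subjects on each site. Section 10.13 allows a site to be terminated once total enrolment is achieved.

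**The concern.** Two sets of figures do not fit together.

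The first is the unit of the sample size. The three groups cover five named areas: axillae, bikini line, thighs, back and abdomen. Section 8.2 gives its figure of 40 per area, but its total of 120 matches three units, not five. With no variance or power in the section, the count of 40 is most of what the justification contains, and it is used to claim sufficiency for safety as well as efficacy. A reader told that each area has 40 subjects may credit back or abdomen with twice the evidence the design yields there, or more.

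The second is recruitment. A fixed quota at every site, multiplied by the stated number of sites, gives twice the stated total. The quota is also the only rule that produces equal groups. If it is not followed everywhere, nothing else in the protocol secures 40 per group.

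**Working it through.** **Inputs.** N = 120, five areas, 40 per area (8.2). Three groups, one group per subject, four subjects per group per site (7.5). 20 sites (synopsis). Ceiling of 12 per site (synopsis, 2, 5.1).

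**Reproducing 120.**
- By treatment group: 3 x 40 = 120. This matches.
- By site: 10 sites x 12 = 120. This matches, but with 10 sites rather than 20.

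The protocol does not state 40 per group. It follows from 120 / 3 under the equal quota.

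**Point 1: subjects per area.** Axillae and bikini line are treated in the same subjects, so they need only one set of 40.

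*Group 3 read as back or abdomen.*
- Needed for 40 in every area: 40 (axillae and bikini line) + 40 (thighs) + 40 (back) + 40 (abdomen) = 160, which exceeds 120.
- Unequal groups do not help, because four separate sets of 40 always total 160.
- With 40 per group: back + abdomen = 40, so the smaller of the two is at most 40 / 2 = 20. An even split gives 20 and 20; a 25:75 split gives 10 and 30.

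*Group 3 read as back and abdomen in every subject.*
- 40 + 40 + 40 = 120, and all five areas have 40 for treatment exposure. Section 8.2 is then right on exposure.

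As an illustration of the difference for safety, assume that no subject has a given adverse event. The one-sided 95% upper bound on its rate is 1 - 0.05^(1/n):
- n = 40: 1 - 0.05^(1/40) = 7.2%.
- n = 20: 1 - 0.05^(1/20) = 13.9%.

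The protocol plans no such bound; it only shows what halving the area size does.

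**Point 2: sites.**
- Quota per site: 4 x 3 = 12.
- At 20 sites: 20 x 12 = 240, or 240 / 3 = 80 per group, against 120 and 40.
- Spreading 120 over 20 sites: 120 / 20 = 6 per site, and 6 / 3 = 2 per group per site, against the rule of 12 and 4.

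**The case against.** **On the unit.** The strongest reply is that area in the second sentence of 8.2 is a loose word for treatment group. The bracketed total shows that 40 was multiplied by three, and the mention of five areas stands in a different sentence. That is probably how the wording arose, but it concedes the point: the stated unit is wrong and should read as group. A second reply is that group 3 subjects may have both back and abdomen treated. The documents do not rule this out. Calling it one large area, where group 1 is called two areas joined by a conjunction, favours either-or without settling it, so Point 1 stays conditional.

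**On sites.** Twelve is a ceiling, so 20 sites and 120 subjects are compatible on their own. Section 10.13 would let ten sites fill at four per group and the rest close. This stands: a reader might infer that no site can follow both 7.5 and the synopsis, and that is too strong, because an individual site can. What remains is that 7.5 applies the quota to each site, and sites closed early would not meet it.

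**Stronger readings to avoid.**
- A reader might infer that the hair-count endpoint has even fewer subjects per area, since 7.4.2.2 uses the singular: "The appropriate treatment area will be decided" and "The template will be placed directly on the skin, in the area to be treated". The section does not say whether axillae and bikini line each have a count site, and its template has a field for the treatment area, which is compatible with one sticker per area. This is a separate question of clarity, and no figure here rests on it.
- A reader might infer that the efficacy analysis is underpowered. Section 8.2 gives nothing from which power could be computed, and 8.3 specifies no test by area. Section 8.3 also does not say whether groups are pooled.
- A reader might infer that N must rise to 160 or 240. The documents do not show that either was intended.

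**Conclusion.** Both points hold, at moderate weight.

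1. The stated 40 per anatomical area is 40 per treatment group under the three equal groups of 7.5. On the either-or reading of group 3, back and abdomen share 40, at least one has 20 or fewer, and 120 is 40 short of the 160 that 40 in every area would need. On the both-areas reading the claim holds for treatment exposure, and the text should say so.
2. The fixed quota at 20 sites gives 240, twice the stated 120. The ceiling and the site-closure clause soften this but do not remove it.

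The first result assumes equal groups, which rest on the four-per-group rule; the shortfall against 160 does not depend on that assumption. The second takes the quota in 7.5 and the 20 sites in the synopsis as written. The consequence is limited to the per-area size claimed in 8.2 and to the enrolment plan; no analysis specified in 8.3 changes.

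**What to change.** These are text changes, with no added subjects.

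- In 7.5, define whether the back / abdomen group means either area or both in each subject.
- In 8.2, restate both sentences, including the one that counts five areas, as 40 subjects per treatment group (3 x 40 = 120). Say that axillae and bikini line come from the same 40 subjects and, if group 3 is either-or, that back and abdomen share 40.
- Reconcile the number of sites, the site quota and the total across the synopsis and 7.5. Two ways that keep 120: 10 sites of 12 with four per group, or 20 sites averaging 6 with a central cap of 40 per group in place of the per-site quota.

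The cost is a less favourable stated size for back and abdomen if they are alternatives, and central tracking of enrolment by group if the cap is used.
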